Food restriction in adolescence is not only difficult to accomplish, but it also raises concerns about growth and development. A medication approved for the treatment of obesity in the adolescent age group that improves body composition by reducing body fat and increasing lean tissue without needing to restrict food intake would be a useful tool for physicians who address the treatment of obesity in adolescents. Albuterol is a medication, approved for ages 6 and older, used for the treatment of asthma and has also been shown to increase muscle strength and lean body mass in children with spinal muscular atrophy (Skura, Fowler et al. 2008) and in healthy young men during an exercise training program.(Caruso, Hamill et al. 2005) A drug approved for the treatment of adolescent obesity that increases lean tissue, decreases fat tissue and can be given in conjunction with lifestyle modifications would be welcomed by both pediatricians who treat these adolescents and by adolescents who are stigmatized by their obesity.

A provisional patent has been submitted by Pennington Biomedical Research Center to protect the combination of caffeine and albuterol in a 1:25 ratio for synergistically

increasing muscle mass and decreasing fat mass as a potential treatment for obesity in adolescents.

Inclusion and Exclusion Criteria

Participants will come to an initial screening visit (SV) after an overnight fast of 10 hours. Consent and assent will be obtained and the inclusion/exclusion criteria below will be assessed. Screening labs (CBC; chem 26 including glucose, BUN, creatinine, sodium, chloride, potassium, carbon dioxide, uric acid, total protein, phosphorus, albumin, calcium, magnesium, total bilirubin, CPK, LDH, AST, ALT, alkaline phosphatase, GGT, amylase, iron, cholesterol, triglycerides, HDL, LDL; fasting insulin; and urinalysis with urine pregnancy test as needed) and an EKG will be done to help determine eligibility.

Inclusion

- -Healthy males or females with a BMI ≥ 95th percentile
- -Between 12 and 17 years of age inclusive
- -Tanner Stage III and above

Exclusion

- -Weigh less than 50 kg
- -Have a family history of sudden death or hypertrophic cardiomyopathy
- -Have a history of unexplained syncope
- -Have a marked baseline prolongation of QT/QTc interval (QTc interval >450 ms), a history of additional risk factors for torsade de pointes (e.g., heart failure, hypokalemia, family history of Long QT Syndrome), or use concomitant medications that prolong the QT/QTc interval
- -Have history of asthma, hypertension, thyroid disease, or significant neurologic disease such as seizure disorder
- -Are pregnant, planning to become pregnant, or nursing. Females who are sexually active must be using adequate contraception.
- -Take a medication known to affect weight or body composition like systemic glucocorticoids, atypical anti-psychotics, or weight loss medications
- -Take beta-stimulators or beta-blockers on a regular basis
- -Take stimulants for attention deficit disorder
- -Take monoamine oxidase inhibitors, tricyclic antidepressants, or diuretics
- -Take any chronic medication that has not had a stable dose for 1 month or longer
- -Have type 1 or type 2 diabetes
- -Have any significant cardiac disease (such as heart failure, arrhythmias, or valve disease), uncontrolled pulmonary disease, chronic liver disease, chronic kidney disease, or chronic infectious disease
- -Have any significant psychiatric illness that is unstable or untreated such as bipolar disorder, severe depression, or severe anxiety
- -Have a history of suicidal ideation
- -Have an allergy or hypersensitivity to albuterol
- -Are unwilling to discontinue caffeine-containing products while in the study
- -Are deemed unfit to participate in the study based on evaluation by the medical investigator

Number of Subjects

We expect to enroll 20 adolescents to complete studies in 12 adolescents.

Recruitment Methods

The Recruitment Core is responsible for recruiting potential participants for clinical trials from a population that includes a wide range of people of various ages, ethnic backgrounds and with varying degrees of health. The PBRC recruitment team creates and implements individualized, trial-specific advertising and awareness campaigns, including mass media, traditional advertising, and novel methods including social media, digital, and email marketing. All advertising and awareness are approved by the PBRC IRB to ensure ethical and disclosure standards are met. The PBRC database may also be utilized to find potential subjects for this study.

Study Timelines

Depending on scheduling, the total duration of this study is approximately 10 weeks (including screening) with 8 weeks of treatment. Following screening evaluations, eligible subjects will be randomized to the study intervention as follows: either 8 weeks of treatment with placebo or 8 weeks with the combination of caffeine/albuterol. The estimated length of time to complete the entire study (from enrollment of the first subject to completion of the last subject) is 6 months with study analysis to be complete 6 months after the completion of the last subject.

Study Endpoints

The primary endpoint is to assess the effect of the combination of caffeine and albuterol on fat mass and lean body mass via DXA scan in obese adolescents.

The secondary endpoints include assessing the effect of the combination of caffeine and albuterol on hunger and satiety as well as the safety of the combination of caffeine and albuterol compared to placebo.

Procedures Involved

This study will be a double-blinded, randomized, placebo-controlled, pilot study in which subjects will be randomized to receive either placebo or a combination of Albuterol 4 mg and Caffeine 100mg three times per day orally for a total of 8 weeks. Each subject will continue on the study intervention for the entire duration of treatment.

Overview

Prior to study entry the following procedures will be performed:

- obtain written informed consent
- record medical history
- verify conformance with entry criteria

Twelve obese adolescents will be recruited through general advertisement and physician referrals. The study will consist of 6 total study visits. The first study visit will be a screening visit and include a medical history/physical, an electrocardiogram, and screening labs. The Beck Depression Inventory will also be used to screen for depression in these adolescents. A psychologist is available on site to assess anyone whose score indicates further evaluation is necessary, and the adolescent may be referred to outside sources if deemed necessary. Adolescents who qualify will return

for a baseline visit fasting within one month of the screening visit. The adolescent will have a DXA scan for body composition as well as a Visual Analog Scale (VAS) test for hunger and satiety. A parent will complete a Vanderbilt Assessment Scale for ADHD to determine if the adolescent has any signs of attention deficit or hyperactivity at baseline. The adolescent will then be randomized to either the placebo or treatment group (Albuterol 4 mg tid and Caffeine 100 mg tid orally) in a 1:1 ratio. The albuterol and caffeine will be obtained from Spectrum Chemical, Letco Medical, or a similar approved distributor where the pharmacy acquires FDA approved medications. Albuterol is approved for the treatment of asthma in adolescents (12-18) at 4 mg three or four times a day. Starting with the baseline visit and at every 2 week visit, the adolescent and parent will meet with a registered dietitian certified in pediatric weight management. The information provided will include recommendations on healthy eating, increasing physical activity, and family participation as recommended by the Academy of Nutrition and Dietetics. At week 2, 4, 6, and 8, compliance (via pill counts) and adverse events will be assessed. At the week 4 visit, the screening labs will be repeated along with an electrocardiogram as safety measures. In addition to these assessments, at week 4 and 8, the adolescent will come fasting to clinic and having taken their morning dose of study medication. They willhave a repeat VAS scale for hunger and satiety, and a parent will fill out another Vanderbilt Assessment Scale for ADHD as a safety measure. If there are any concerns based on the Vanderbilt Assessment Scale, the intervention will be stopped and the adolescent will be referred to an appropriate health care provider for further evaluation. At the last study visit after 8 weeks of intervention, the adolescent will have an electrocardiogram, a repeat DXA, and repeat labs to compare with the screening labs. Approximately 7 days (± 2 days) later, someone from the study staff will call the participant to assess for any adverse events while off the study intervention.

Study Evaluations

The following study evaluations will be obtained at the screening visit (SV):

- Body weight, height, body mass index (BMI), vital signs
- Complete medical history and physical examination
- Beck Depression Inventory
- Standard 12-lead EKG
- Urinalysis
- Labs including fasting insulin, Chemistry 26 and CBC (~7.5 mL or 1.5 teaspoons of blood)
- Collection of concomitant medications

The following study evaluations will be obtained at the Baseline visit:

- Body weight, height, body mass index (BMI), vital signs
- Family weight management counseling
- Pregnancy test (if applicable)
- DXA scan for body composition
- Randomization to either study intervention
- Dispensing of study medication
- Visual Analog Scale for hunger and satiety
- Vanderbilt Assessment scale for ADHD
- Collection of concomitant medications

The following study evaluations will be obtained at the Week 2 visit

- Body weight, height, body mass index (BMI), vital signs
- Collection of concomitant medications
- Family weight management counseling
- Dispensing and collecting study medication
- Assessment of tolerability and compliance (via pill counts)
- Assessment of adverse events

The following study evaluations will be obtained at the Week 4 visit

- Body weight, height, body mass index (BMI), vital signs
- Collection of concomitant medications
- Family weight management counseling
- Dispensing and collecting study medication
- Assessment of tolerability and compliance (via pill counts)
- Assessment of adverse events
- Visual Analog Scale for hunger and satiety
- Pregnancy test (if applicable)
- Urinalysis
- Labs including fasting insulin, Chemistry 26 and CBC (~7.5 mL or 1.5 teaspoons of blood)
- Standard 12-lead EKG
- Vanderbilt Assessment scale for ADHD

The following study evaluations will be obtained at the Week 6 visit

- Body weight, height, body mass index (BMI), vital signs
- Collection of concomitant medications
- Family weight management counseling
- Dispensing and collecting study medication
- Assessment of tolerability and compliance (via pill counts)
- Assessment of adverse events

The following study evaluations will be obtained at the Week 8 visit

- Body weight, height, body mass index (BMI), vital signs
- Collection of concomitant medications
- Family weight management counseling
- Collecting study medication
- Assessment of tolerability and compliance (via pill counts)
- Assessment of adverse events
- Pregnancy test (if applicable)
- Urinalysis
- Labs including fasting insulin, Chemistry 26 and CBC (~7.5 mL or 1.5 teaspoons of blood)
- DXA scan for body composition
- Standard 12-lead EKG
- Visual Analog Scale for hunger and satiety
- Vanderbilt Assessment scale for ADHD

The following study evaluation will be done at Week 9 over the phone

• Follow up with the participant, or participant's parent(s)/legal guardian if participant is a minor, to assess for any adverse events that may have occurred after stopping the intervention.

Study Procedures

Whole Body DXA scan (Baseline and Week 8)

This scan measures the amount of bone, muscle, and fat in your body. The scan will be performed using a whole-body scanner. You will be required to wear a hospital gown, to remove all metal-containing objects from your body, and to lie down on the table. A scanner emitting low energy X-rays and a detector will pass along your body. The scan takes approximately 5 to 10 minutes. You will be asked to remain completely still while the scan is in progress. This scan is for research purposes only and not for diagnostic treatment.

Study Schedule

Procedures	SV	Baseline	Week 2	Week 4	Week 6	Week 8	Week 9
Inclusion/Exclusion,	Х						
Consent and Assent							
History and Physical	Х						
Beck Depression Inventory	Х						
Weight, height, vital signs	Х	X	Х	Х	Х	Х	
Collection of concomitant medications	Х	Х	Х	Х	Х	Х	
Family weight management counseling		X	X	X	X	X	
DXA scan for body composition		X				X	
Screening labs: blood draw	Х			Х		Х	
Screening labs: urinalysis	Х	X		Х		Χ	
Urine pregnancy test (if applicable)		Х				Х	
EKG	Х			Х		Х	
Dispense and collect medications		X	X	Х	X	Х	
Tolerability and compliance (pill counts)			Х	X	X	X	
Adverse events			Χ	Х	X	Χ	
Randomization to treatment sequence		X					
Visual Analog Scale for hunger and satiety		X		X		Х	
Vanderbilt Assessment scale for ADHD		X		Х		Х	
Follow up phone call							Х

[#] Each visit has a window of ± 2 days

Power analysis

This is a pilot study and no power analysis was calculated. Data from this study may be used to power a larger study.

Data and Specimen Management

The data management will be conducted by the Pennington Biomedical Research Computing Group. There will be limited access to all data including locked cabinets for paper files and password protected computers for electronic data.

Each participant will be issued an ID number that will be utilized throughout the study. A secure master file linking names, addresses and ID numbers will be maintained in a confidential computer file accessible only to the investigators. Access to data files can be made only with permission of the Principal Investigator. Privacy in the context of this study includes confidentiality of data and personal information. During interviews, measurements, and other study-related activities, the study staff will ensure full privacy of participants and will ensure that the data are stored in a secured area. All study staff must be HIPAA certified.

Statistics

Comparisons will be made between the control and intervention groups using chisquared tests to compare categorical data and t-tests to compare means with 2 time points and analysis of variance for end points with repeated measures with a significant p value of ≤ 0.05 .

Provisions to Monitor the Data to Ensure the Safety of Subjects

Participants and their parents will be instructed on symptoms that should prompt them to contact the site or seek medical attention, such as palpitations or lightheadedness. Adverse events will be monitored every 2 weeks at each study visit. The PI and his coinvestigator will review lab data on a regular basis throughout the study (screening, Week 4, and Week 8) to ensure the safety of each subject. Any significant health problems coming to our attention during the study will be referred to the participant's usual source of medical care, with his/her parents' permission.

A formal IND application has been filed with the FDA and in addition to the reporting requirements set forth by the IRB, additional responsibilities include:

- -Reporting any unexpected fatal or life-threatening suspected adverse reactions to the FDA no later than 7 calendar days after initial receipt of the information
- -Reporting any (1) serious, unexpected suspected adverse reactions, (2) findings from other clinical, animal, or in-vitro studies that suggest significant human risk, and (3) a clinically important increase in the rate of a serious suspected adverse reaction to the FDA and to all investigators no later than 15 calendar days
- Submitting annual progress reports within 60 days of the anniversary of the date that the IND became active (the date clinical studies were permitted to begin)

Withdrawal of Subjects

During the course of the study, participants may be withdrawn from the study for the following reasons:

Unwillingness to participate in the study or cooperate with study staff

 Presentation of significant medical symptoms or abnormal findings such as a prolonged QTc that would warrant termination of study participation to protect the participant's safety

Data that have already been collected during the course of study participation from a withdrawn participant will be used, unless a specific request is otherwise received. Subjects will be notified of their withdrawal via telephone or mail.

Risks to Subjects

General: More serious risks and adverse effects may occur than those listed below. The combination of caffeine and albuterol has not been well studied and adverse effects may be additive or synergistic with the combination. There may be more risks of ingesting additional caffeine products (such as coffee, tea, Coke®, or Red Bull®) and alcohol while in the study. A list of caffeine-containing products to avoid during the study will be provided as a reference. If a dose is missed, the participant should not double up on the dose because of the possible risk of adverse effects.

Caffeine: This can be found in a variety of foods and beverages. Caffeine is a stimulant and may cause increased heart rate, alertness, tremor, and difficulty sleeping. Albuterol: This is a prescription medication that is approved for use in treatment of asthma in children as young as 6 years of age. The most common side effects include: nervousness, tremor, headache, tachycardia, and palpitations.

Blood Draws: There is the possibility of infection and/or pain and bruising at the vein on your arm where the needle is inserted. Aseptic (sterile) technique and trained personnel minimize these risks.

Electrocardiogram (EKG or ECG): There are minimal risks associated with this test. There is a small possibility there may be some redness or irritation while cleaning the skin prior to applying the electrodes or if you happen to be allergic to the adhesive on the electrodes.

Whole Body DXA scan: The amount of radiation used for this procedure is very small. The radiation dose for this scan is equivalent to the radiation you are naturally exposed to in the environment in less than one day. Scans will not be performed on any subject who is pregnant, and all females will be provided with a urine pregnancy test prior to the scan.

Visual Analog Scale for hunger and satiety: This is a well-validated scale to assess hunger and satiety and carries little to no risk.

Vanderbilt Assessment scale for ADHD: There is little to no risk in filling out this questionnaire. This is used by pediatricians and parents to identify a child's risk for attention deficit/hyperactivity disorder. This will serve as an additional safety measure and will be obtained at baseline and then every 4 weeks.

Potential Benefits to Subjects

While in the study, participants may demonstrate an improvement in body composition with decrease in fat mass and increase in lean body mass. These changes may not be sustained once the participant stops the intervention.

Vulnerable Populations

Adolescents between the ages of 12 and 17 who are in the midst of puberty will be enrolled in the study. All participants will be provided with an age appropriate assent form in additional to the parental consent form. All questions and concerns will be addressed by the study staff.

Sharing of Results with Subjects

Individual participant results will not be provided; however, results from the study will be submitted for manuscripts in scholarly journals and presentations. All study reports will present only aggregated data to minimize the risks that a participant can be identified form their participation in the study. As required by the FDAAA this study will be registered on ClinicalTrials.gov.

Setting

Potential participants will be recruited utilizing the recruiting services (Recruitment Core) of the PBRC. All research procedures will be performed at the PBRC, namely, in the Outpatient Clinic.

Resources Available

Pennington Biomedical Research Center has had a good track record with recruiting a population of overweight/obese adolescents for a variety of intervention studies. Potential participants come from a variety of sources such as traditional advertising, physician referral, word of mouth, etc.

The clinical research staff are well trained and have to undergo a variety of certifications before performing assessments on study participants.

Medical personnel are available onsite to conduct study visits as well as oversee any adverse events. Psychologists are available on call should the need arise for further evaluation based on screening inventories or other assessments.

Prior to the opening of the study, a start up meeting is held with all of the relevant clinical cores to ensure that proper coordination is in place prior to the first screening visit.

Compensation

Each participant will receive \$25 after the completion of the baseline visit, week 2, week 4, and week 6 visits, and \$50 after the week 8 visit for a total of \$150.

Provisions to Protect the Privacy Interests of Subjects

All attempts will be made to maintain a subject's privacy. Safeguards such as password protected computers and networks have been put in place in order to limit access to subject data. These data will be maintained until the results may be published and will only be accessible by study personnel.

Subjects will be given ample time to read over the consent, ask questions, and agree to participate in the research study. Subjects may decline answering questions they are

not comfortable with. Each procedure will be explained to the subject before it is performed.

Compensation for Research-Related Injury

No compensation will be provided for research-related injury.

Economic Burden to Subjects

All study-related tests and procedures will be at no cost to the subject. The subject will incur transportation costs in getting to PBRC.

Consent Process

The P.I. or one of the designated clinic staff will obtain informed consent from the parent/guardian and separate assent from all of the minor participants in the outpatient clinic during the screening visit. Ample opportunity will be given for the parent/guardian and the minor participant to review the consent/assent and to ask any questions prior to signing any forms.

A parent/guardian is to provide his or her identification along with the child's birth certificate in order to verify the relationship to the minor participant.

As a greater than minimal risk study with the prospect of direct benefit, one parent may provide consent for the minor participant to engage in the study.

Drugs or Devices

Both interventions will be stored in the research pharmacy located in the outpatient clinic. This is locked at all times and only accessible to limited personnel via a key card. The research pharmacist will maintain an inventory of study drugs. Appropriate dispensation of study drug will be confirmed with a second clinic staff member to ensure correct drug is being provided to the correct participant.

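### VAS hunger and satiety: the repeated-measures ANOVA names no treatment term and appears to count the pre-randomisation baseline as a time level; a baseline-adjusted model with one named contrast is a cheap, low-priority improvement

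*Combined protocol and SAP*

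**What the plan says.** The analysis plan is one sentence in the Statistics section. It compares control and intervention by chi-squared tests for categorical data, "t-tests to compare means with 2 time points" and "analysis of variance for end points with repeated measures", at a 0.05 significance level. It does not say which ANOVA term tests treatment, whether baseline is an outcome level or a covariate, or what happens when a visit is missing. It does not mention VAS.

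Study Endpoints lists "assessing the effect of the combination of caffeine and albuterol on hunger and satiety" among the secondary aims. The Overview under Procedures Involved describes DXA and VAS at the baseline visit and continues: "The adolescent will then be randomized to either the placebo or treatment group". For weeks 4 and 8 it adds: "They willhave a repeat VAS scale for hunger and satiety". The Study Schedule confirms VAS at baseline, week 4 and week 8, and DXA at baseline and week 8.

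On numbers, Number of Subjects states "We expect to enroll 20 adolescents to complete studies in 12 adolescents", while the Overview states "Twelve obese adolescents will be recruited through general advertisement and physician referrals". Withdrawal of Subjects keeps a withdrawn participant's existing data in use unless a request is made otherwise. The Power analysis section says that none was done.

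**The concern.** DXA has two time points only if baseline is one of them. By the same count VAS has three, so it falls to the ANOVA with a pre-randomisation value as one level. No treatment effect can exist at that level, and the answer then depends on which term is reported. A group main effect averages a true zero with the two post-treatment differences. A group-by-time test avoids this but spreads its power over two degrees of freedom. Neither uses baseline as a covariate, which is usually its best use in a randomised comparison.

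Classical repeated-measures ANOVA also needs a complete row per participant, so a week-4 VAS without a week-8 VAS would be left out. That would sit badly with the commitment in Withdrawal of Subjects.

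At stake are precision on a secondary endpoint with about 6 completers per arm, and a choice of test left open until the data are seen. The DXA primary endpoint is not affected.

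**Working it through.** The plan gives no power, effect size or SD, so there is no figure to reproduce.

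**Inputs from the documents.** 12 completers (Number of Subjects) and 1:1 allocation (Overview), taken as n = 6 per arm; significance level 0.05; VAS at three visits.

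**Assumed, because the documents give none.** Two-sided test, SD 1 at each visit, equal correlation ρ of 0.3, 0.5 or 0.7 between visits, and the effects shown below.

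**1. Group main effect, baseline as a level.** For a constant effect d it estimates (0 + d + d)/3 = 2d/3; 1.2 SD becomes 0.80 SD. The variance is (2/n)(1 + 2ρ)/3, on 10 df. At ρ = 0.5, SE = √(0.333 × 0.667) = 0.471, and 0.80/0.471 = 1.70 gives 34% power.

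**2. Group-by-time.** F test on 2 and 20 df with noncentrality (n/2) × SS/(1 − ρ), where SS is the sum of squared deviations of the visit effects about their mean. For (0, 1.2, 1.2), SS = 0.96; at ρ = 0.5, 3 × 0.96/0.5 = 5.76 gives 50% power.

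**3. Baseline-adjusted week 4/8 average.** Residual variance is (1 + ρ)/2 − ρ², the small-sample factor is 1 + 1/(2n − 4) = 1.125, on 9 df. At ρ = 0.5, SE = √(0.333 × 0.50 × 1.125) = 0.433, and 1.2/0.433 = 2.77 gives 69% (70% by simulation).

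**4. Week 8 by plain baseline-adjusted ANCOVA.** Residual variance is 1 − ρ², with the same factor and df. At ρ = 0.5, SE = √(0.333 × 0.75 × 1.125) = 0.530, and 1.2/0.530 = 2.26 gives 52%.

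Power (%) with complete data, at ρ = 0.3/0.5/0.7:

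| Effect at weeks 4, 8 (SD) | Group main effect | Group-by-time | Adjusted average | Week-8 ANCOVA |
|---|---|---|---|---|
| 1.2, 1.2 | 40/34/29 | 37/50/73 | 65/70/83 | 45/52/69 |
| 0.5, 0.5 | 11/10/9 | 10/12/17 | 17/18/23 | 12/14/18 |
| 0.3, 1.2 (builds) | 19/16/14 | 31/42/64 | 32/35/45 | 45/52/69 |
| 1.2, 0.3 (fades) | 19/16/14 | 32/42/63 | 32/34/45 | 8/8/9 |

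The week-8 column and the main-effect entries in the last two rows come from the formulas. The rest are simulated and agree with the formulas to about one point.

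**5. Week-4-only participants.** The gap between 20 enrolled and 12 completing is 8, but the number with week 4 and no week 8 is not given. At screening, "Consent and assent will be obtained and the inclusion/exclusion criteria below will be assessed", and randomisation comes later, so some of the 8 may be screen failures. The range is 0 to 8. Holding 12 completers fixed, with losses at random and 1.2 SD at both visits, keeping week-4 values changes power for the average as follows:
- 0 participants: no gain
- 2 participants: 65/70/83% to 71/76/89%
- 4 participants: 66/70/82% to 76/80/92%
- 8 participants: 65/71/83% to 83/88/96%

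These runs used a compound-symmetry model on equal-variance data, so they are approximate for the model recommended below. For a week-8 contrast, even 8 such participants add only 2 to 6 points.

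**6. Covariance structure.** Compound symmetry forces equal variances at weeks 4 and 8. With 6 per arm, ρ = 0.5 and no effect, a week-8 contrast from such a model rejects in 7.0% and 8.8% of trials when the week-8 SD is 1.25 and 1.5 times the week-4 SD. In the reverse case it rejects in 3.1% and 1.8%. Plain week-8 ANCOVA and the average contrast stay near 5%.

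**The case against.** The strongest reply is that most of the apparent damage comes from choices the plan does not make. Much of that stands.

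- A reader might infer that the planned analysis will understate the VAS effect by a third. The documents do not support this: no term is named, and group-by-time, the usual one, is not diluted.
- A reader might infer that up to 8 of 20 participants' data will be discarded. The plan never says complete-case, Withdrawal of Subjects points the other way, and the number and timing of losses are not given. The statement that twelve are recruited makes the count less certain still.
- A reader might infer that the mixed model is better whatever happens. It is not: the average ties with or loses to group-by-time when the effect builds or fades, and a week-8 contrast has almost no power when it fades.
- An ANOVA on weeks 4 and 8 alone would avoid dilution, but it fits the plan poorly. If baseline were not counted, VAS would have two time points and go to the t-test.

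It is also fair that 1.2 SD is a large effect for appetite. Background reports unchanged food intake with the combination, in rodents, and at 0.5 SD no method is informative. The same sentence of the plan would cover weight, vital signs, laboratory values and the Vanderbilt scale; VAS is singled out because it is a named secondary efficacy endpoint.

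The order of baseline VAS and randomisation rests on the Overview. The baseline list in Study Evaluations puts randomisation above VAS, but it is a list of evaluations and not a sequence.

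What the reply does not remove is that the term, the role of baseline and the missing-value rule are open, and that baseline and week-4 data already being collected can be used better at almost no cost.

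**Conclusion.** The point holds as a low-priority efficiency improvement. The ANOVA names no treatment term and, by inference from how DXA fits the two-time-point rule, counts a pre-randomisation baseline as a level.

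Against group-by-time, a baseline-adjusted week 4/8 average gains about 28, 20 and 10 percentage points at correlation 0.3, 0.5 and 0.7 (65 − 37, 70 − 50, 83 − 73) if the effect is 1.2 SD at both visits. At 0.5 SD the gain is 6 to 7 points from a very low base. If the effect builds or fades, that gain is absent or reversed. The two-thirds dilution applies only if the group main effect were reported, and loss of week-4 data only if the ANOVA were run on complete cases.

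Effect size, SD, correlation, time course and timing of losses are all assumptions. This is a secondary endpoint in a pilot without a power calculation.

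**What to change.** In the Statistics section, state the following for week-4 and week-8 VAS, separately for hunger and for satiety:

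- A REML linear mixed model with arm, visit, arm-by-visit and baseline VAS, visit-specific variances (unstructured 2 × 2 covariance) and Kenward-Roger degrees of freedom.
- Inclusion of every randomised participant with at least one post-baseline VAS, with the number who have none reported by arm and the missing-at-random assumption stated.
- One treatment contrast per scale, named before unblinding. This is the week 4/8 average or, if the effect is expected to build, week 8 by plain baseline-adjusted ANCOVA. The choice is the sponsor's.
- No week-8 contrast from a compound-symmetry model, because its type I error ran from about 2% to 9% when the visit SDs differed by up to 1.5-fold.

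If the sponsor prefers ANOVA, state its time levels, its treatment term and how missing VAS values are handled.

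The cost is a few lines of text and one degree of freedom for baseline, with no new visits or measurements. The named contrast has less power than the 2-df group-by-time test if the time course is not the one assumed. Choosing week-8 ANCOVA also means that week-4-only participants do not contribute to that contrast, though the calculation above suggests they would add little to it.
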